2.4 Other Safety Measures

Summaries of proportions of participants experiencing any elevated and clinically significant BUN or creatinine findings between Visit 1 and Visit 3 are provided.

Also summarized are proportions of participants retreated with IV antibiotics. Retreatment is defined as any additional IV antibiotics administered 3 or more days after the stop date of the initial IV antibiotic treatment for pulmonary exacerbation and prior to Visit 3 (e.g. rescue treatment or treatment of the new pulmonary exacerbation).

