STUDY DESIGN	This randomized, controlled, open-label study is designed to evaluate the efficacy and safety of differing durations of IV treatment, given in the hospital or at home for a pulmonary exacerbation in adult patients with CF. The study will assess the non-inferiority of 10 days versus 14 days treatment duration among ERR subjects and the superiority of 21 days versus 14 days treatment duration among the subjects who do not meet the definition of ERR (non-ERR; NERR) Subjects will undergo pulmonary function testing (spirometry) and complete a respiratory symptom score [Chronic Respiratory Infection Symptom Score (CRISS)] at initiation of IV treatment (Baseline/ Visit 1) and at Day 7-10 (Visit 2). At Visit 2, subjects will be allocated to groups ERR or NERR based on their initial clinical response as determined by the change in forced expiratory volume in 1 second (FEV ₁ ; percent of predicted) and CRISS from Baseline and then randomized to an IV treatment duration (nested within group). ERR subjects [$\geq 8\%$ predicted improvement in FEV ₁ from Baseline (Visit 1) to Visit 2 and CRISS reduction of ≥ 11 points from Baseline (Visit 1) to Visit 2] will be randomized 1:1 to either 10 days or 14 days total IV antibiotic treatment duration. Remaining (NERR)

	
subjects will be randomized 1:1 to receive either 14 or 21 days total IV antibiotic treatment duration. All subjects will be evaluated again at Visit 3, 14 days following scheduled completion of IV antibiotic treatment.

DURATION OF SUBJECT PARTICIPATION AND DURATION OF STUDY
	
Dependent on the treatment arm, subjects will be on study from 24 to 35 days:
 
 ▪ Treatment prior to randomization: 7 – 10 days ▪ Treatment post-randomization: 
 ○ ERR-10 subjects: 0 to 3 days = 10 days (± 1 day) total IV treatment ○ ERR-14 subjects: 4 to 7 days = 14 days (± 1 day) total IV treatment ○ NERR-14 subjects : 4 to 7 days = 14 days (± 1 day) total IV treatment ○ NERR-21 subjects: 11 to 14 days = 21 days (± 3 days) total IV treatment ▪ Follow-up: 14 days after end of scheduled IV antibiotic treatment (± 2 days) 
The total duration of the study is expected to be approximately 42 months: 41 months for subject recruitment and 1 month for final subject follow-up.

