2.1 Risk / Benefit Assessment

Treatment-Associated Risks:

This is an interventional study that will dictate the duration of IV antibiotics for the treatment of pulmonary exacerbation. There can be risks associated with the randomization as patients might be allocated to a duration of antibiotic therapy that may be too short or too long. The potential risk of an insufficient duration of antibiotics is an early relapse of the exacerbation, although surveys of CF clinicians reveal that a majority consider any new treatment for an exacerbation, at any time after the previous treatment, to be a new event rather than a relapse. The potential risks of an excess duration of antibiotics include unnecessary cost as well as the potential for injury attributed to the treatment, specifically drug toxicity (e.g., antibiotic-associated nephrotoxicity, ototoxicity, neurotoxicity, and/or vestibular toxicity, *C. difficile* colitis due to broad spectrum

antibiotic use) or a complication related to the indwelling IV catheter (e.g., thrombus). Clinicians are keenly aware of these potential complications as part of standard therapy and monitor these risks routinely. Generally, intravenous antibiotics used to treat acute pulmonary exacerbation in CF are all well tolerated, and CF patients have extensive experience receiving repeated courses of intravenous antibiotics for acute pulmonary exacerbation.

It is noted that the duration of antibiotics will be 10, 14 or 21 days, which are consistent with current durations used to treat patients (CFFNPR data). Of note, 50% of patients will be randomized to 14 days of IV antibiotics, which is the most frequently used duration (CFFNPR data) and the most frequently reported duration by CF clinicians (survey data, not published). In addition, the randomization is based upon the initial response to treatment such that the duration of antibiotics is even more likely to be consistent with current treatment practices [i.e., patients with a robust response will tend to get a shorter duration (10 vs 14 days) while those with a more sluggish response will tend to get a longer duration (14 vs. 21 days)]. This randomization allocation should mitigate the risks of inappropriately short or long durations as they will be tied to the initial patient response and are consistent with common practice among CF clinicians.

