9.2.2 Clinical Chemistry

Results for BUN and creatinine used to determine care for the initial pulmonary exacerbation and any BUN and creatinine tests performed as part of clinical care during the study will be recorded on the CRF.

Results for serum glucose performed as part of clinical care for the initial pulmonary exacerbation and during the study will be recorded on the CRF (if more than one is performed on a given day, only one test per day will be recorded).

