11 ADVERSE EXPERIENCE REPORTING AND DOCUMENTATION

11.1 Adverse Events

An adverse event (AE) is any untoward medical occurrence in a subject that is participating in this clinical investigation that is related to study participation (treatment arm assignment), study procedures, or any other significant AE as determined by the investigator.

AEs are defined as new or worsening of signs or symptoms, including clinically significant abnormal clinical laboratory values, that occur after randomization (Visit 2) until Visit 3.

An unexpected AE is one of a type not identified in nature, severity, or frequency or of greater severity or frequency than expected.

The Investigator will probe, via discussion with the subject, for the occurrence of AEs and record the information in the site's source documents. AEs will be recorded in the subject CRF.

AE Severity

The National Cancer Institute's Common Terminology Criteria for Adverse Events (CTCAE) Version 4.0, as modified for cystic fibrosis, should be used to assess and grade AE severity, including laboratory abnormalities judged to be clinically significant. The modified criteria can be found in the Study Reference Binder. If the experience is not covered in the modified criteria, the guidelines shown in Table 1 below should be used to grade severity. It should be pointed out that the term "severe" is a measure of intensity and that a severe AE is not necessarily serious.

Table 1. AE Severity Grading

Severity (Toxicity Grade)	Description
Mild (1)	Mild; asymptomatic or mild symptoms; clinical or diagnostic observations only; intervention not indicated
Moderate (2)	Moderate; minimal, local or noninvasive intervention indicated; limiting age-appropriate Instrumental activities of daily living (e.g., preparing meals, using the telephone, managing money)
Severe (3)	Severe or medically significant but not immediately life-threatening; hospitalization or prolongation of hospitalization indicated; disabling; limiting self care activities of daily living (e.g., bathing, dressing, feeding self, using toilet, taking medications)

Life-threatening (4)	Life-threatening consequences; urgent intervention indicated
Death (5)	Death related to AE

AE Relationship to Treatment Arm Assignment

The relationship of an AE to the treatment arm assignment should be assessed using the following the guidelines in Table 2.

Table 2. AE Relationship to Treatment Arm Assignment

Relationship to Treatment	Comment

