1.4 Definition of the Analysis Populations

Enrollment and screening summaries will be generated using all screened participants. All compliance and safety analyses will be performed using an intent-to-treat (ITT) population, defined as all subjects randomized at Visit 2. The ITT population will also be used to generate all NERR primary efficacy analyses. The primary ERR analyses will be performed using per-protocol population (PP), defined as subjects in the ITT population who have no protocol violations.

2. Results

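### The SAP's renal laboratory summary starts at Visit 1, before randomization, which dilutes the comparison between duration arms

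*SAP*

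**What the plan says.** The dedicated renal measure is in SAP 2.4 (Other Safety Measures) and is worded as follows: "Summaries of proportions of participants experiencing any elevated and clinically significant BUN or creatinine findings between Visit 1 and Visit 3 are provided". That section gives no numeric threshold, does not say who decides clinical significance, sets no reference value and plans no test. It does not itself say that the proportions are split by arm. I read it so because SAP 1.2 has safety data summarized by duration group.

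The surrounding text is as follows.

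- **Population.** SAP 1.4: "All compliance and safety analyses will be performed using an intent-to-treat (ITT) population, defined as all subjects randomized at Visit 2".
- **Time before randomization.** Protocol Synopsis, duration of participation: "Treatment prior to randomization: 7 – 10 days".
- **Adverse event window.** Protocol 11.1 counts new or worsening findings, "including clinically significant abnormal clinical laboratory values, that occur after randomization (Visit 2) until Visit 3". SAP 2.3 tabulates emergent abnormal laboratory values among the adverse events, by duration arm.
- **Source of the data.** Protocol 9.2.2: "any BUN and creatinine tests performed as part of clinical care during the study will be recorded on the CRF". Appendix 1 schedules no BUN or creatinine test; it only collects clinical care results.
- **Why renal findings matter.** Protocol 2.1 lists "antibiotic-associated nephrotoxicity, ototoxicity, neurotoxicity, and/or vestibular toxicity" among the risks of too long a course.

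**The concern.** Random assignment can influence only what happens after Visit 2. The SAP 2.4 window opens 7 to 10 IV days earlier. A patient whose creatinine is raised at Visit 1, or rises on Day 5 and settles by Day 7, counts as an event in whichever arm is drawn later. The plan's own adverse event definition starts at randomization, so the two renal outputs of one report would use different windows with no reason given.

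The primary objective has a safety half: ERR-10 is to be as safe as ERR-14, and NERR-21 is to be safe compared with NERR-14. The shared days make up 70% to 100% of a 10-day course (7/10 to 10/10), 50% to 71% of a 14-day course and 33% to 48% of a 21-day course. Much of what SAP 2.4 counts therefore says nothing about the duration assigned.

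**Working it through.** **Plan's own figures.** The documents give no event rate, effect size or power for the renal measure. Protocol 15.7 supplies only arm sizes, and its power statements reproduce with power = Φ(δ / (σ√(2/n)) − 1.96):

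- NERR: 2.5 / (9·√(2/285)) = 3.32, giving 91.2% (stated 91%).
- ERR: 3.5 / (9·√(2/155)) = 3.42, giving 92.8% (stated 93%).

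So 285 and 155 per arm are used below.

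**Dilution formula.** Let q be the risk of a finding before randomization (equal in both arms in expectation) and p the risk afterwards. The Visit 1 to Visit 3 risk is 1 − (1 − q)(1 − p). The risk difference is therefore (1 − q) times the post-randomization difference. The ratio moves much more, because q adds to both numerator and denominator.

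**Illustration (assumed: 0.5% risk per IV day, none off IV, Visit 2 at Day 8.5).** Risk over d days = 1 − 0.995^d. Then q = 1 − 0.995^8.5 = 4.2%, and 1 − q = 0.958. IV days after Visit 2 are 1.5, 5.5 and 12.5 for 10-, 14- and 21-day courses.

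| Comparison | Window | Risks | Difference (points) | Ratio | Power |
|---|---|---|---|---|---|
| ERR-10 v ERR-14 | after randomization | 0.75% v 2.72% | 1.97 | 3.6 | 26% |
| ERR-10 v ERR-14 | Visit 1 to 3 | 4.89% v 6.78% | 1.89 | 1.4 | 11% |
| NERR-14 v NERR-21 | after randomization | 2.72% v 6.07% | 3.35 | 2.2 | 50% |
| NERR-14 v NERR-21 | Visit 1 to 3 | 6.78% v 9.99% | 3.21 | 1.5 | 28% |

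Check: 0.958 × 1.97 = 1.89 and 0.958 × 3.35 = 3.21.

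Power is the two-sided 0.05 comparison of proportions, Φ((d − 1.96·se0)/se1), with se0 pooled and se1 unpooled. For NERR:

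- After randomization: (0.0335 − 1.96 × 0.01717)/0.01712 ≈ −0.01, giving 50%.
- Visit 1 to 3: (0.0321 − 1.96 × 0.02322)/0.02318 = −0.58, giving 28%.

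Since SAP 2.4 plans no test, power here is only a yardstick for precision.

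**Values already raised at Visit 1.** If 5% are raised (assumed), each Visit 1 to 3 risk becomes 1 − 0.95(1 − risk). ERR is 9.6% v 11.4%, ratio 1.2. NERR is 11.4% v 14.5%, ratio 1.3.

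**Range (constant hazard per IV day, total risk 5% to 15% by the end of the longer course).**

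- NERR, randomization at Day 7 to 10: ratio 1.95 to 2.73 after randomization against 1.46 to 1.49 from Visit 1; power 24% to 76% against 16% to 40%.
- ERR, randomization at Day 7 to 8.5: ratio 2.28 to 3.64 against 1.37 to 1.39; power 16% to 52% against 9% to 18%. At Day 10, ERR-10 has no IV days left and the post-randomization ratio is undefined.

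**What a narrower window does not cure.** Visit 3 falls 14 days after scheduled completion, so nominal follow-up from Visit 2 (Day 7 to 10) is 24 minus 10 to 7 = 14 to 17 days for 10-day treatment, 28 minus 10 to 7 = 18 to 21 for 14-day, and 35 minus 10 to 7 = 25 to 28 for 21-day, visit tolerances aside. Testing depends on clinical care and may also differ. With equal true risk of 10% and detection of 50% v 70% (assumed), the observed risks are 5% v 7%, a ratio of 1.4 with no real difference.

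**The case against.** The strongest reply is that a post-randomization renal comparison already exists. Clinically significant laboratory abnormalities are adverse events under Protocol 11.1 if they occur after randomization. SAP 2.3 tabulates emergent ones by arm, severity and relationship, with Poisson rate ratios by organ class. Adverse event incidence is the protocol's named safety endpoint (5.2), while SAP 2.4 is an untested supplement. This stands, and it is why the point is minor. It does not dispose of it: the adverse event route depends on judgement in an open-label trial and does not use the recorded values.

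The second reply is that events before randomization balance in expectation, so the difference in proportions is nearly intact. That also stands. The loss is in the ratio and in precision.

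A reader might infer three stronger things that the documents do not support.

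- **That the unblinded investigator decides which results count.** SAP 2.4 names no judge, and Protocol 11.1 does not say who judges laboratory values. The supportable point is that threshold and judge are undefined. A judgement made before Visit 2 cannot be influenced by an arm not yet assigned.
- **That untested patients are counted as normal.** No denominator is stated, and SAP 1.3 refers to table shells that are not in the text available.
- **That a longer course would be made to look renally safe.** More testing or longer follow-up in the longer arm would push its proportion up, not down.

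**Conclusion.** The point holds as a minor one. By its stated window, SAP 2.4 mixes findings that assignment cannot affect into the comparison between arms, out of line with the protocol's own adverse event window. The effect is dilution: under the assumed 0.5% per IV day, the risk difference shrinks by about 4%, while the ratio falls from 3.6 to 1.4 in ERR and from 2.2 to 1.5 in NERR, with a matching loss of precision. The renal rates are assumptions; the window and the shared 7 to 10 days are not. The direction and size of any bias from unequal testing or from judgement cannot be settled from the documents.

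**What to change.** In SAP 2.4:

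1. Make the by-arm measure new or worsened BUN or creatinine results dated after randomization through Visit 3, relative to the last value on or before randomization. Show results from Visit 1 to randomization separately.
2. Base the event on the recorded value: the CF-modified CTCAE grade where it covers the test, otherwise a numeric threshold fixed in advance. Keep BUN as well as creatinine. Give the clinical significance call as a second row and state who makes it. The modified criteria sit in the Study Reference Binder, so their coverage must be checked there.
3. Report by arm the number tested, tests per patient and follow-up time after randomization, with proportions among those tested and among all randomized.
4. Give risk differences beside ratios, and refer to the adverse event tables in SAP 2.3 so that the two renal outputs can be read together.

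The cost is SAP wording and one revised table. No new tests are needed, since clinical care results are already recorded; confirm that the CRF holds their dates. The price is fewer events and an incomplete tested denominator, which the table would show openly.

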2.5 Summary of Primary Efficacy Endpoint

The primary endpoint is the absolute change in percent predicted FEV₁ from Visit 1 (Baseline) to two weeks after scheduled completion of IV antibiotics (Visit 3). The primary endpoint is compared between treatment durations within ERR and NERR groups using Analysis of Variance (ANOVA) adjusted for dichotomous randomization strata: Visit 1 FEV₁, number of IV-treated exacerbations in prior year, location of IV administration by Visit 2, and use of systemic corticosteroids by Visit 2. The treatment effect for each group (ERR and NERR) (estimated via adjusted ANOVA least squares means) is presented along with corresponding 95% confidence intervals. Observed treatment effect and the 95% CI provide primary inference and evidence of non-inferiority, superiority, or lack thereof in both the ERR and NERR groups.

ERR Group (PP population): The non-inferiority of ERR-10 versus ERR-14 is tested against a 3.5 % predicted non-inferiority margin with a one-sided 0.025 level of significance.

NERR Group (ITT population): The superiority of NERR-21 versus NERR-14 is tested with a two-sided 0.05 level of significance.

The primary analysis for ERR is repeated in the ITT population, and the primary analysis for NERR is repeated in the PP population.

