8 STUDY TREATMENTS

8.1 Method of Assigning Subjects to Response Group and Treatment Arms

All eligible subjects will undergo pulmonary function testing (spirometry) and complete a respiratory symptom score (CRISS) at Baseline (Visit 1) and at Day 7-10 (Visit 2). At Visit 2, subjects will be allocated to either the ERR or NERR group based upon their initial clinical response as determined by the change from Baseline in FEV₁ (percent of predicted as determined by GLI equations)^{18,19} and CRISS and then randomized to a treatment arm (duration nested within response group). The spirometry and CRISS measures must be present and entered into EDC for both Baseline (Visit 1) and Visit 2 for randomization to occur.

ERR subjects [$\geq 8\%$ predicted improvement in FEV₁ from Baseline (Visit 1) to Visit 2 and CRISS reduction of ≥ 11 points from Baseline (Visit 1) to Visit 2] will be randomized 1:1 to either 10 days (ERR-10) or 14 days (ERR-14) total IV antibiotic treatment duration while remaining subjects not meeting the ERR threshold will be randomized 1:1 to receive either 14 (NERR-14) or 21 (NERR-21) days total IV antibiotic treatment duration. A minimum of 310 subjects (155 per duration arm) will be allocated to the ERR group and a minimum of 570 subjects (285 per duration arm) to the NERR group. Randomization will occur by a predetermined scheme. Within each response group, subjects will be stratified by Visit 1 FEV₁ (FEV₁ < 50% of predicted versus $\geq 50\%$ predicted), number of IV-treated exacerbations in prior year (0-1 versus 2+ in prior year), location of IV treatment by Visit 2 (exclusively home versus any hospital nights), and use of systemic corticosteroids by Visit 2.

Randomization will occur centrally using a web based randomization system linked to the electronic data capture (EDC) system. Only authorized site personnel are given access to the EDC system. Authorized site personnel will enter subject eligibility information as well as any information needed for randomization stratification. The system will provide the appropriate authorized site personnel with a randomization assignment for that subject that matches a specific treatment duration.

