15.7 Sample Size

ERR Group:

A non-inferiority design to show that the change in FEV₁ between Visit 1 and Visit 3 in the ERR subjects who received 10 days of treatment (ERR-10) is no more than 3.5 % predicted less than ERR subjects who received 14 days treatment (ERR-14) requires 310 subjects (155 per arm) who complete the study. STOP pilot data indicate a mean change (SD) in FEV₁ between baseline and Day 28 in patients with an early response to be 12.5 % predicted, 95% CI [9.5, 15.6]. Assuming two-sided alpha =0.05, standard deviation =9.0% predicted and the true difference between two groups is zero, the ERR study has 93% power to detect a 3.5 % non-inferiority margin which preserves 72% of the treatment effect or 63% of the lower bound of treatment effect observed in the STOP pilot.

NERR Group:

A superiority design to show that the change in FEV₁ between Visit 1 and Visit 3 in NERR subjects who received 21 days treatment (NERR-21) is at least 2.5 % predicted greater than NERR subjects who received 14 days treatment (NERR-14) requires 570 subjects (285 per arm) who complete the study. STOP pilot data indicate a mean change (SD) in FEV₁ between baseline and Day 28 in patients without an early response to be 4.0 % predicted, 95% CI [1.9, 6.1]. Assuming two-sided alpha =0.05 and standard deviation =9.0% predicted, the NERR study has 91% power to detect a 2.5% or greater increase in FEV₁ among those treated with 21 days compared to 14 day IV antibiotic. A 2.5% improvement was chosen to represent a minimal clinically important difference in lung function to justify the additional burden and potential toxicity of 21 days of treatment versus 14. It is important to note that statistical significance can be shown at the end of the superiority NERR study with a smaller treatment effect than 2.5%.

Observed treatment effect (mean difference in absolute FEV₁ change) and the 95% CI will provide primary inference and evidence of non-inferiority, superiority, or lack thereof in both the ERR and NERR groups. Motivated to ensure conclusive results, this study was designed to provide sufficiently narrow 95% CIs at the end of the trial (ERR 95% CI half-width=2%;

NERR 95% CI half-width=1.5% when both SD=9%).

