Because this trial will enroll a slightly different patient population (including home IV, excluding patients who receive <7 days of IV antibiotics), a blinded, interim assessment of change in FEV₁ % predicted and variance (pooled) will be performed and expected sample size may be adjusted for either the ERR or NERR groups.

Based on STOP pilot data, we anticipate 1:2 allocation of subjects into the ERR and NERR groups. To meet the enrollment goal of a minimum of 310 completed ERR subjects and a minimum of 570 completed NERR subjects, we will screen approximately 1330 subjects. Of these, we expect approximately 1236 subjects will be enrolled and randomized (assuming a conservative 7% drop-out rate between Visit 1 and Visit 2) and a minimum of 310 completed ERR subjects and a minimum of 570 completed NERR subjects (assuming an approximate 4% drop-out rate between Visit 2 and Visit 3).

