1.1 Study Rationale and Design

In patients with cystic fibrosis (CF) who are experiencing a pulmonary exacerbation, a strong desire among clinicians to reduce treatment durations (and reduce cost, inconvenience, and potential toxicities) is in conflict with belief that patients not responding robustly to treatment might benefit from extending treatment. An assessment taken after one week of treatment has been demonstrated to predict the overall response, especially for those with an early robust improvement (Early Robust Response; ERR). These patients are often treated with shorter courses of intravenous (IV) antibiotics in clinical practice and will likely experience no additional benefit from an extended IV treatment (although this has never been objectively studied). Patients who have a less robust early response to treatment often receive extended treatments in a belief that better overall responses are attained. Although the additional clinical benefit of prolonged courses of IV antibiotics should outweigh potential risks of toxicity, treatment burden, and increased resource utilization, these relationships have also never been objectively tested.

This randomized, controlled, open-label study is designed to evaluate the efficacy and safety of differing durations of IV treatment, given in the hospital or at home, for a pulmonary exacerbation in adult patients with CF. The study will assess the non-inferiority of 10 days versus 14 days of treatment among ERR subjects and the superiority of 21 days versus 14 days treatment duration among the subjects who do not meet the ERR definition (non-ERR; NERR).

Subjects will undergo pulmonary function testing (spirometry) and complete a respiratory symptom score [Chronic Respiratory Infection Symptom Score (CRISS)] at initiation of IV treatment (Baseline/ Visit 1) and at Day 7-10 (Visit 2). At Visit 2, subjects will be allocated to groups ERR or NERR based on their initial clinical response as determined by their change in forced expiratory volume in 1 second (FEV₁; percent of predicted) and CRISS from Baseline and then subsequently randomized to an IV treatment duration (nested within group).

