2.13 ERR-14 and NERR-14 Participants

Descriptive comparisons of the two cohorts treated for 14 days (ERR-14 and NERR-14) are performed to characterize associations between early assessments of clinical response (at Visit 2) and after completion of treatment for a PEx (Visit 3). Comparisons of these two groups are performed for baseline characteristics, treatments and outcomes utilizing both the study data and the CFFNPR.

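### Optional precision gain: the primary ANOVA leaves the continuous within-group variation in Visit 1 and Visit 2 ppFEV1 unused, although both values are complete before randomization

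*SAP*

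**What the plan says.** The primary model is the same in SAP 2.5 and protocol 15.3: "Analysis of Variance (ANOVA) adjusted for dichotomous randomization strata". The four strata are Visit 1 FEV1, IV-treated exacerbations in the prior year, location of IV treatment by Visit 2, and systemic corticosteroid use by Visit 2. Protocol 8.1 cuts Visit 1 FEV1 at 50% predicted. No primary-endpoint model in either document has a continuous ppFEV1 term.

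On timing, protocol 8.1 states: "The spirometry and CRISS measures must be present and entered into EDC for both Baseline (Visit 1) and Visit 2 for randomization to occur". Protocol 10.2 also lists spirometry before randomization.

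On prognostic value, SAP 1.1 says: "An assessment taken after one week of treatment has been demonstrated to predict the overall response", and adds that this holds especially for early robust responders. SAP 2.13 plans a descriptive comparison of ERR-14 with NERR-14 to relate Visit 2 response to Visit 3 status.

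On precision, protocol 15.7 says that "this study was designed to provide sufficiently narrow 95% CIs at the end of the trial", with half-widths of 2% (ERR) and 1.5% (NERR) at an SD of 9%. It also plans a blinded pooled variance assessment.

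**The concern.** Both primary conclusions are read from a 95% confidence interval, so its width decides how clear the answer is. Randomization takes place at Visit 2, which makes Visit 1 and Visit 2 ppFEV1 true pre-randomization covariates. They are complete for every randomized subject, and therefore also for the ERR per-protocol set. Adjusting for them introduces no post-randomization bias and leaves the target, a difference in mean change, as it is.

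The ERR/NERR split already captures part of the early response. Within each group, however, subjects still differ in how far their FEV1 moved by Visit 2, and the planned model treats them alike. If that remaining variation predicts Visit 3, the same subjects could give a narrower interval. This would count most if the SD exceeds 9.0, a possibility the planned variance assessment allows for. No conclusion is wrong without the change.

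**Working it through.** **1. The plan's own figures.** Inputs from protocol 15.7: SD 9.0; two-sided 0.05 (the same interval as the SAP's one-sided 0.025 for ERR); ERR 155 per arm with margin 3.5; NERR 285 per arm with difference 2.5.

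- Half-width = 1.96 × 9 × √(2/n): ERR 2.00, NERR 1.48.
- Power = Φ(δ/SE − 1.96), with SE = 9 × √(2/n): ERR 92.8%, NERR 91.2%.

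These match the stated 2%, 1.5%, 93% and 91%.

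**2. Effect of the covariates.** Let R² be the share of within-group outcome variance, beyond the strata, explained by continuous Visit 1 and Visit 2 ppFEV1. The SD becomes 9 × √(1 − R²), and the equivalent sample size under the planned model is n/(1 − R²).

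**3. What R² might be.** The documents give none, so this step is an assumption. Protocol 15.7 gives pilot mean changes of 12.5 (95% CI 9.5 to 15.6) with an early response and 4.0 (1.9 to 6.1) without.

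- Difference D = 12.5 − 4.0 = 8.5.
- SEs are 6.1/3.92 = 1.556 and 4.2/3.92 = 1.071. The SE of D is √(1.556² + 1.071²) = 1.89, so the 95% CI is 4.8 to 12.2.

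The calibration takes early FEV1 change and CRISS reduction as bivariate normal and applies the joint cut. Assumed: correlation 0.2–0.4; 40–50% passing the FEV1 cut; one third passing both (the protocol's 1:2 split); within-group SD 9; Visit 1 level unrelated to outcome. The outcome is driven either by early FEV1 change alone or by FEV1 and CRISS equally, scaled so that the group means differ by D. R² is then the share explained by early FEV1 change within each group.

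- D = 8.5: ERR 0.075–0.22, NERR 0.08–0.44. The high ends need FEV1 alone to drive the outcome and 50% to pass the FEV1 cut. With FEV1 and CRISS driving it equally, R² is about 0.08–0.10.
- D = 4.8: R² scales by (4.8/8.5)² = 0.32, giving ERR 0.024–0.07 and NERR 0.027–0.14.

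A simpler check, splitting on FEV1 change alone at D = 8.5, gives about 0.10 (ERR) and 0.15 (NERR), inside these ranges.

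**4. Results at the minimum sample size, SD 9.**

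| Group | R² | Half-width | Power | Equivalent n per arm |
|---|---|---|---|---|
| ERR | 0 | 2.00 | 92.8% | 155 |
| ERR | 0.02 | 1.98 | 93.3% | 158 |
| ERR | 0.10 | 1.90 | 95.0% | 172 |
| ERR | 0.22 | 1.77 | 97.2% | 199 |
| NERR | 0 | 1.48 | 91.2% | 285 |
| NERR | 0.02 | 1.46 | 91.8% | 291 |
| NERR | 0.10 | 1.40 | 93.8% | 317 |
| NERR | 0.44 | 1.11 | 99.3% | 509 |

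At R² of 0.08–0.10 the intervals are 4–5% narrower (√0.92 = 0.959; √0.90 = 0.949).

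**5. At the expected enrolment.** Protocol 15.7 says "we expect approximately 1236 subjects will be enrolled and randomized", with about 4% later loss. That is 1236 × 0.96/3/2 = 198 per arm in ERR and 1236 × 0.96 × (2/3)/2 = 396 in NERR. Under the planned model, power is then about 97% in each group and the half-widths are 1.77 and 1.25.

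**6. Validity.** In a simulation of NERR (285 per arm, 4000 runs, R² 0.10 and 0.25), two-sided type I error was about 4.5–4.8% with or without the covariates. Mean half-width fell from 1.48 to 1.41 and 1.28.

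**The case against.** The strongest reply is that nothing here is broken: adjusting for the randomization strata is a defensible primary model and it delivers the stated precision. That stands, and it is why this is only an optional change.

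Three stronger readings are tempting, and the documents do not support them.

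- A reader might infer that the plan ignores early response. It does not: each comparison is made within groups defined by that response. Only the remaining continuous part is unused.
- A reader might infer that the documents show prediction within ERR or NERR. They do not. The SAP 1.1 statement concerns the one-week assessment overall, which uses FEV1 and CRISS together. SAP 2.13 compares ERR-14 with NERR-14, and the pilot means are also a between-group contrast. Turning them into a within-group R² needs the model in step 3, whose correlation, pass rate and outcome weights are not in the documents.
- A reader might infer a large gain in both groups. ERR members have all passed the FEV1 cut, so less variation remains there. In NERR the upper figure needs the most favourable assumptions.

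It is also fair to say that the change touches more than one SAP paragraph. SAP 1.2 plans formal monitoring with by-arm efficacy at 50% and 75%, and protocol 15.6 refers to a monitoring plan with stopping rules.

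**Conclusion.** This is an optional improvement, not an error. The planned ANOVA is valid and meets its stated power and half-widths. Adding continuous Visit 1 and Visit 2 ppFEV1 keeps the estimand and would narrow the intervals by an amount the documents cannot fix.

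Under the assumed calibration, R² is about 2–22% in ERR and 2–44% in NERR. Half-widths would be about 1.98–1.77 instead of 2.00, and 1.46–1.11 instead of 1.48. Power would be about 93.3–97.2% and 91.8–99.3%. If FEV1 and CRISS matter equally, the intervals are about 4–5% narrower at the pilot difference.

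The range runs from the lower confidence limit of the pilot difference to its point estimate. It is not a confidence interval, and the upper limit of 12.2 was not used. At the low end the gain is trivial. With about 1236 randomized, any benefit is mainly in interval width, because power is already about 97%. The documents do not show what continuous Visit 1 ppFEV1 would add by itself; it belongs in the model because early change is the difference between the two visits.

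**What to change.** In SAP 2.5, prespecify as primary an ANCOVA of the Visit 1 to Visit 3 change in ppFEV1 on treatment duration, continuous Visit 1 ppFEV1, continuous Visit 2 ppFEV1 and the four strata, fitted separately in ERR and NERR. Keep the strata-only ANOVA as a sensitivity analysis. Use the same model in the DMC monitoring plan, so that the interim and final analyses agree.

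Fix the model before the 50% by-arm efficacy look, since SAP 1.2 gives the closed reports to the study biostatisticians. The documents do not show whether that look has taken place. If it has, a statistician without by-arm access should fix the model before database lock.

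The cost is a SAP revision, alignment of the monitoring plan, and 2 degrees of freedom: 310 − 6 = 304 becomes 302 in ERR, and 570 − 6 = 564 becomes 562 in NERR. No new data are needed, and protocol 15 lets the SAP carry changes to the analysis plan. The planned blinded pooled variance assessment could report the residual SD with and without the two covariates, which would show the size of the gain without by-arm data.
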